3.7 Sample size

Due to the exploratory nature of this trial a formal sample size calculation is not performed.

We plan to include n = 12 female subjects.

3.8 Recruitment

Potentially relevant subjects will be invited directly to participate by using advertisement and/or announcements of the Clinical research Center for Hair and Skin Science. The volunteers will be contacted by telephone.

4 Methods: assignment of interventions

4.1 Assignment of interventions

After the baseline measurements are completed, opaque envelopes will be opened to assign the treatment order. In order to minimize bias, the product allocation will be randomized. A computerized simple 1:1:1:1 randomization scheme for four study visits will be applied for the sacral skin for $n = 12$ subjects. An example of a possible allocation is displayed in Table 4.

Table 4. Example for order of experimental interventions for the sacral skin

Subject number	Dressing application order visits 1, 2, 3, 4
1	C → A → D → B
2	B → D → C → A
3	A → C → D → B
4	D → A → B → C
5	B → A → C → D
6	A → C → B → D
7	B → C → A → D
8	...
9	...
10	...
11	...
12	C → B → D → A

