2.2 Aims

The overall aim of this study is to measure the effects of Mepilex® Border Sacrum on the skin structure and function during mechanical loading compared to (1) no dressing, (2) ALLEVYN Life Sacrum and (3) Optifoam® Gentle Liquitrap Sacrum.

The following objectives are determined:

(1) To measure the changes of skin temperature, stratum corneum hydration, erythema and skin roughness, (2) to evaluate clinical signs of pain and erythema and (3) to determine IL-1alpha and total protein of the sacral skin before loading (baseline) and after three and a

half hours loading with or without application of a dressing (Mepilex® border, ALLEVYN Life Sacrum, Optifoam® Gentle Liquitrap Sacrum).

3. Methods: Participants, interventions, and outcomes

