3.4 Study procedures and interventions

Volunteers will come to the study centre for four visits. In between, there are at least 3 weeks to prevent possible carry over effects. Therefore, the entire duration of one subject will be at least 9 weeks. The duration of one study visit per subject is approximately 5 hours. After four visits, each volunteer will have received each intervention once (A, B, C and D, see Table 1).

Table 1. Experimental interventions for the sacral skin

Intervention	Dressing
A	None
B	Mepilex® Border Sacrum
C	ALLEVYN Life Sacrum
D	Optifoam® Gentle Sacrum

After giving informed consent, subjects will lie down in supine position on a standard hospital mattress for a maximum of 10 minutes. Then subjects will turn around into prone position. Two fields of equal size (each 2cm x 2.5cm) will be marked with a skin pen, one for the baseline and one for the follow-up measurements. If an erythema has occurred at the sacral area during the 10 minutes in supine position, the investigational site will be marked within the reddened skin area. In case of no erythema, the test area will be identified by feeling the most protuberant point at sacrum. After marking the measurement area the subjects will acclimatize under standardized room temperature and humidity conditions (22±2°C, 40 to 60% rel. humidity) for 30 minutes with having the sacral skin uncovered. Subjects may lay (on the side) or sit during this period but must make sure that the investigational area is uncovered. After that, subjects will move into prone position and the following baseline measurements will be conducted according to CRC standard operating procedures (SOPs):

- (1) Measurement of skin surface temperature
- (2) Measurement of SC hydration (SCH)
- (3) Measurement of Erythema index (EI)
- (4) Visioscan images to measure Rz, Ra
- (5) Cyanoacrylate skin surface stripping (CSSS), to determine IL-1alpha and total protein of the sacral skin.

In addition to the instrumental measurements, erythema and pain will be evaluated clinically.

The measures of skin surface temperature, SCH and EI will be performed three times per measuring round. Two duplicate Visioscan images will be taken. CSSS will be performed at the end.

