After the baseline measurements a randomization envelope will be opened to allocate the subject to one of the intervention groups A, B, C or D (see Table 1). The dressings (B, C, D) will be applied or the skin will be left uncovered (A), followed by a 3.5 hours loading period. The subject will lie in supine position on a standard hospital mattress. Every 30 minutes the head of the bed will be elevated to 45° for five minutes. During these five minutes, the participants will be instructed to bend their knees and to drag the feet repeatedly forth and back 10 times. Then the head of bed will be moved back again and the subjects can relax. The whole exercise will be done six times, after 0.5, 1, 1.5, 2, 2.5 and 3 hours.

After 3.5 hours loading time in supine position the subjects will move into prone position. In case of interventions B, C or D the dressings will be removed. Then all skin measurements and CSSS will be conducted again. After the end of the measurements and procedures, subjects will leave the study site. They will come back for another three times completing the remaining interventions.

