3.6 Variables and outcomes

Due to the explorative nature of this study, no distinction between primary, secondary or other variables is made (Table 3).

Table 3. Variables and outcomes

Name	Method and metric
Skin phototype	
 • Classification according to Fitzpatrick (nominal)
Height	
 • Measurements in the CRC • m (metric)
Weight	
 • Measurements in the CRC • kg (metric)
Age	
 • Checking by looking at the ID card • metric
Sacral pain	
 • Subjects' self-report • Pain (yes/no) (nominal) • Time to pain reporting in minutes (metric)
Erythema	
 • Visual inspection • VAS (metric)
Skin surface temperature	
 • Skin thermometer based in infrared technique (Courage and Khazaka Electronic GmbH) • °C (metric)
SCH	
 • Noninvasive instrumental measure using the Corneometer CM 825 (Courage and Khazaka Electronic GmbH) • Arbitrary units, A.U. (metric)
EI	
 • Noninvasive instrumental measure using the Mexameter MX18 (Courage and Khazaka Electronic GmbH) • Arbitrary units, A.U. (metric)
Rz, Ra, Rmax	
 • Visioscan VC 98 (Courage and Khazaka Electronic GmbH) • µm (metric)
Cytokines	
 • Cyanoacrylate skin surface stripping (CSSS) (or another sampling method) • IL-1, total protein in pg/µg • ELISA

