5.2 Statistical methods

Demographic characteristics will be described using numbers, proportions, means and standard deviations. Metric outcomes will be described using mean and spread parameters per intervention and time point. Baseline and follow-up parameters will be compared descriptively.

6 Methods: monitoring

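### Simple randomisation in 4.1 does not ensure that the four interventions are balanced over visits in 12 women, and 5.2 does not account for visit (low priority)

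*Combined protocol and SAP*

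**What the plan says.** Section 3.4 gives each woman four visits and each intervention once, and states that between visits "there are at least 3 weeks to prevent possible carry over effects". Section 3.7 plans 12 women. For the order of interventions, section 4.1 says "A computerized simple 1:1:1:1 randomization scheme for four study visits will be applied for the sacral skin". Section 4.2 puts each woman's order in a sealed envelope and withholds the scheme from the investigators. Neither section mentions blocks, a Latin square or any limit on how often an intervention may fall on a given visit.

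The unit of the draw is not described uniformly. Section 3.4 says "After the baseline measurements a randomization envelope will be opened to allocate the subject to one of the intervention groups", whereas 4.1 and 4.2 speak of an order. Since no intervention is repeated in a woman, drawing the whole order at once or drawing visit by visit gives the same distribution.

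On analysis, section 5.2 says "Metric outcomes will be described using mean and spread parameters per intervention and time point". The time points in section 2.2 are before and after loading, not visits 1 to 4. The objective there is "To measure the changes of skin temperature, stratum corneum hydration, erythema and skin roughness", but 5.2 does not name change from the same visit's baseline as the quantity compared between interventions. No visit summary or visit term is planned.

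**The concern.** Receiving each intervention once fixes the total at 12 applications per intervention. It does not fix the visits on which they fall. With a simple scheme, one dressing may by chance be used mostly at early visits and another at late ones. If the response drifts over the nine weeks or more of participation, part of that drift then enters the comparison of the two dressings.

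The exposure is limited. Section 3.4 takes a new baseline at each visit, so additive drift that affects both skin fields equally cancels from change. What remains exposed is:

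- the raw follow-up means that 5.2 describes;
- "Time to pain reporting in minutes (metric", which has no pre-loading value;
- drift in the response to loading itself;
- drift not shared by the baseline field and the follow-up field.

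**Working it through.** The plan gives no figure to reproduce: section 3.7 states that there is no formal sample size calculation, and no visit effect is given anywhere.

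**Inputs from the documents.** 12 women (3.7); 4 interventions, 4 visits, each intervention once per woman (3.4); simple scheme (4.1).

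**Assumptions.** Reading 1: 12 independent draws from the 24 possible orders. Reading 2: 12 different orders out of the 24. Neither is stated. Drift is taken as linear, k within-subject SDs per visit, with k = 0.1, 0.25 or 0.5; none of these comes from the documents.

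**Step 1, imbalance of one named contrast.** An intervention's visit number is uniform on 1 to 4, with variance 15/12 = 1.25. Two interventions in the same woman have covariance −1.25/3. The variance of their difference is 2 × 1.25 + 2 × 1.25/3 = 10/3.

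- Reading 1: SD of the mean over 12 women = sqrt((10/3)/12) = sqrt(10/36) = 0.53 visits.
- Reading 2: finite-population factor (24 − 12)/(24 − 1) = 12/23, so SD = sqrt(10/36 × 12/23) = 0.38 visits.

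In 200,000 simulated lists per reading, the absolute difference is 0.5 visits or more in 39% (reading 1) and 23% (reading 2). The median is 0.33 and 0.25 visits.

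**Step 2, effect on an unadjusted contrast.** The SE of a contrast is sqrt(2/12) = 0.41 SD. With V = 10/36 = 0.278 or V = 0.145, the ratio of root mean squared errors is sqrt(1 + k²V/(2/12)).

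| Drift k per visit | Reading 1 | Reading 2 |
|---|---|---|
| 0.1 SD | +1% | +0.4% |
| 0.25 SD | +5% | +3% |
| 0.5 SD | +19% | +10% |

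The last row is extreme: it means 3 × 0.5 = 1.5 SD between visits 1 and 4. At the reading 1 median imbalance, a drift of 0.1 or 0.25 gives an error of 0.33 × 0.1 = 0.03 or 0.33 × 0.25 = 0.08 SD, against the SE of 0.41 SD.

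**Step 3, adjusting for visit without changing the list.** In a model with woman, visit and intervention, the variance of a contrast relative to 2/12 averages about 1.11 (reading 1) or 1.05 (reading 2) over simulated lists. That is about 5% or 2% in SE. With each intervention 3 times at each visit the ratio is exactly 1.00.

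**Step 4, a balanced list is feasible.** 12 is a multiple of 4, so 3 per intervention per visit is possible. The 8 orders shown in Table 4 can be completed, for example with ADBC, CDAB, DBAC and DBCA, to 12 different orders with 3 in every cell.

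**Step 5, cost in predictability.** With 3 of each intervention at visit 1 in fully random order, someone tracking the counts guesses the visit-1 intervention correctly with probability 51%, 59% and 100% for women 10, 11 and 12. The expected number correct over all women is 5.3, against 12 × 0.25 = 3.0 under simple randomisation.

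**Step 6, dropout.** Removing 1 or 2 women from a four-sequence Latin square in all possible ways gives an average variance penalty of 0.8% or 1.9% for visit adjustment. The same enumeration on the 12-order list of step 4 gives the same rounded values.

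**The case against.** The strongest reply is that 4.1 may already intend balance. Each woman receives every intervention once anyway, so a 1:1:1:1 ratio for four visits adds information mainly if it describes allocation at each visit. That is a fair reading, but the word simple counts against it and no restriction is stated. It softens the point to this: balance is not ensured by the text as written.

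The second reply is that the gain is small. The study is exploratory, has no primary outcome and plans only description. Section 3.4 standardises room climate and acclimatisation at each visit, which limits one plausible source of drift. This stands, and it is why the point has low priority. The exploratory aim removes the need for tests; it does not remove the value of comparable means.

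Three stronger readings are tempting and not supported:

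- **That the comparison is biased.** Random orders favour no intervention on average; the issue is extra chance error in one realised list.
- **That Table 4 shows imbalance.** It is labelled an example, four rows are not filled in, and those rows can be completed to exact balance. It is evidence neither way about the real list.
- **That carry-over is uncontrolled.** Section 3.4 provides at least three weeks between visits, and nothing in the documents shows this to be too short.

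**Conclusion.** The point holds as a cheap improvement, not as an error that endangers the study. As written, 4.1 leaves balance over visits to chance and 5.2 does not account for visit. The chance difference in mean visit for one contrast has SD 0.53 or 0.38 visits, depending on how the orders are drawn. The consequence in outcome units cannot be computed because the documents give no visit effect. Under the assumed linear drift of 0.1 to 0.25 SD per visit, it is a loss of about 0.4% to 5% in root mean squared error for an unadjusted contrast, and less for within-visit change where the drift is shared by both skin fields.

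**What to change.** Low priority, but it has to be done before the first subject, because the list cannot be repaired once envelopes are in use.

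1. **Section 4.1.** Replace the simple scheme by a computer-generated list restricted so that each intervention occurs exactly 3 times at each visit. Preferably use 12 different orders, for example three Latin squares that share no order. A single four-sequence square used three times would show unblinded staff repeated orders by the fifth woman. Shuffle the 12 orders over the whole list, not square by square: blocks of four would raise the expected correct visit-1 guesses to 3 × (1/4 + 1/3 + 1/2 + 1) = 6.25. Table 4 can stay as an example. The details of the restriction can remain with the data manager, in line with 4.2. If balance per visit was intended all along, one sentence saying so is enough here.
2. **Section 5.2.** Describe the interventions by within-woman change from the same visit's baseline, with estimates adjusted for visit. Intervals suffice; no tests are needed. With the balanced list this costs no precision if all women complete. Time to pain has no baseline, so it gains from the balanced list rather than from the change score.

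**Cost.** The same 12 women and 48 visits, a different list, one sentence in 4.1 and a short paragraph in 5.2. The downside is the late-list predictability in step 5. A guess could influence only what precedes the first envelope (eligibility, consent, first baseline; section 4.3), since under 4.1 and 4.2 the whole order is known once that envelope is opened. Exact balance is lost if women withdraw, at an average variance penalty of about 1% to 2% for one or two losses.

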4.2 Allocation concealment

During the trial preparation the data manager, who is not involved in the trial and uses appropriate software, will create this randomization scheme independently. The scheme will not be revealed to the investigators. Sequentially numbered opaque sealed envelopes containing the randomized intervention order will be used.

4.3 Allocation implementation

The batch of sequentially numbered envelopes is stored at the CRC. Envelopes are opened after confirming eligibility, provision of informed consent and after the first baseline measurement.

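### As written, 4.1 to 4.3 disclose the full four-visit order after the first baseline, so staff can know the dressing before up to 36 of 48 baselines; one labelled envelope per visit is a cheap, minor improvement

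*Combined protocol and SAP*

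**What the plan says.** Four places in the protocol bear on when the allocation becomes known.

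- **4.1 Assignment of interventions:** once baseline is complete, "opaque envelopes will be opened to assign the treatment order". Table 4 shows what an order is: one row per woman, covering visits 1 to 4.
- **4.2 Allocation concealment:** "Sequentially numbered opaque sealed envelopes containing the randomized intervention order will be used". The same section adds: "The scheme will not be revealed to the investigators".
- **4.3 Allocation implementation:** "Envelopes are opened after confirming eligibility, provision of informed consent and after the first baseline measurement".
- **3.4 Study procedures and interventions:** "After the baseline measurements a randomization envelope will be opened to allocate the subject to one of the intervention groups A, B, C or D". The account of that visit ends: "They will come back for another three times completing the remaining interventions".

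Three further points set the context. Section 4.4 leaves subjects, study assistants and researchers unblinded; only the data manager is blinded. Section 3.4 has two skin fields marked before the measurements, "one for the baseline and one for the follow-up measurements", and erythema is also judged by eye on a VAS (Table 3). Section 5.2 summarises outcomes by intervention and time point and compares baseline with follow-up descriptively.

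**The concern.** The plan takes care to open the envelope only after baseline. This keeps knowledge of the coming dressing out of the baseline measurements. If the envelope holds the whole order and is opened once, that protection covers visit 1 only. At visits 2, 3 and 4 the people who mark the fields and score the skin can already know what will be applied.

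Two steps leave room for judgement. One is deciding which of the two marked fields is baseline and which is follow-up: 3.4 fixes the site but not the role of each field. The other is the visual erythema score. The field decision also determines where the instrument readings are taken. If either step shifted with knowledge of the dressing, the baseline-to-follow-up comparison could shift by dressing, and comparing dressings is the aim in 2.2.

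**Working it through.** **Inputs.** 12 women (3.7). Four visits, with each of the four interventions received once (3.4). Staff unblinded (4.4). The plan gives no figure of its own to reproduce.

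**Is there a baseline at every visit?** The protocol does not say so outright, but three things support it. Section 5.2 summarises outcomes for each intervention at each time point. Section 4.3 speaks of a first baseline, which implies later ones. Section 3.4 gives one length for all visits: "The duration of one study visit per subject is approximately 5 hours". The timed steps add up as follows:

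- 10 min supine + 30 min acclimatization + 210 min loading = 250 min.
- 300 − 250 = about 50 min for marking and two rounds of measurement.
- A visit without the supine step, acclimatization and baseline would take at most 210 + 50 = 260 min (4.3 h), short of the stated 5 h.

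This is supportive, not proof.

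**Baselines at which the coming dressing is certain**

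- Total: 12 × 4 = 48.
- Full order opened after the visit 1 baseline: 12 × 3 = 36 (75%).
- One envelope per visit: 12 × 1 = 12 (25%), because the fourth intervention follows from the first three.
- Difference: 36 − 12 = 24 (50%), namely visits 2 and 3.

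**Allowing for guessing.** With one envelope per visit, three interventions remain at visit 2 and two at visit 3. The chance of a correct guess at visits 1 to 4 is therefore 1/4, 1/3, 1/2 and 1.

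- Per-visit envelopes: 12 × (1/4 + 1/3 + 1/2 + 1) = 25 expected correct of 48.
- Full-order envelope: 12 × (1/4 + 1 + 1 + 1) = 39 of 48.
- Gain: 39 − 25 = 14 of 48 (29%).

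All counts assume that every woman completes four visits; each missed later visit lowers them.

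**The case against.** The strongest reply has four parts.

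**Section 3.4 need not conflict with 4.1 to 4.3.** It opens with consent, so it can be read as describing the first visit, with a single envelope opened once and the remaining interventions following at later visits. A reader might infer a flat contradiction between the sections. The text does not support that; it supports an ambiguity that a short edit would settle. This part stands.

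**A full-order envelope is a coherent choice.** Every woman receives all four interventions, so knowing the order cannot change which ones she gets. A reader might infer that randomization or concealment at entry has failed. Neither has: the order is still hidden until eligibility, consent and the first baseline are complete. What is lost is only the protection of later baselines.

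**The route to bias is narrow.** Temperature, hydration and erythema index are instrument readings taken in triplicate, the skin images are duplicated, and the cytokines are assayed. Erythema is also measured by instrument. The field question can be closed by a field rule whatever the envelope holds. Follow-up measurements stay unblinded at all 48 visits in any case. All of this stands and is why the point is minor. It does not remove the reason to keep a safeguard the plan already uses at visit 1.

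**Section 4.2 withholds the scheme from the investigators.** That may mean only the master list. No section keeps an opened order from those who take the measurements. Equally, no section says that whoever opens the envelope also takes the measurements, so the count is of what staff can know, not of what they will know.

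**Conclusion.** The point holds as a minor, inexpensive improvement. If 4.1 to 4.3 are followed as written and a baseline is taken at each visit, the coming dressing can be known before up to 36 of 48 baselines, and opening after baseline protects visit 1 alone. One envelope per visit reduces certainty to 12 of 48 and expected correct guesses from 39 to 25.

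Two stronger conclusions are tempting but not supported. One is that the change would hide 24 baselines: it makes them uncertain, and they stay guessable at 1/3 and 1/2. The other is that the baselines will be biased: the figures count disclosure, and the documents give no basis for computing the size of any bias. The trial is exploratory, with no primary outcome and a descriptive analysis, which also limits the weight of the point.

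The conclusion rests on the plain reading of 4.1 to 4.3, on a baseline at every visit, on full attendance, and on there being no SOP that already fixes the fields or restricts who sees an opened order.

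**What to change.** 1. **Sections 4.1 to 4.3 and 3.4.** Use 48 opaque sealed envelopes, each labelled with subject number and visit number and holding only that visit's intervention. State in all four sections that an envelope is opened only after field marking and all baseline measurements of that visit, and that the first is opened only once eligibility and consent are also confirmed. This aligns the wording as well.
2. **Section 3.4.** Fix in advance, by the same rule at all four visits, which marked field is baseline and which is follow-up, or cite the SOP that already does so. This closes the field-choice route whatever the envelope contains.

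If the sponsor prefers to keep the full-order envelope, 3.4 should say so plainly and the protocol should state who may see the opened order. The second change is still worth making.

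**Cost.** The data manager prepares 36 more envelopes (48 instead of 12), and a few sentences change. If this happens after ethics approval, the committee is informed under 7.2. There is a small risk of drawing the wrong envelope, which the subject-and-visit label controls. Visit 4 stays deducible and follow-up stays unblinded.
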